## 2.5 Study Design

This is an open-label, randomized, three-arm, directly observed therapy, pharmacokinetic study of TAF-FTC PrEP among low-risk HIV-uninfected non-pregnant cisgender women. HIV-uninfected non-pregnant cisgender women at low risk for HIV will be randomly assigned to 1 of 3 dosing frequencies of DOT TAF-FTC PrEP (**Figure 3**): 2, 4, or 7 doses per week to help differentiate poor and modest from perfect adherence (**Figure 3**).

Enrollment will continue until 54 non-pregnant evaluable participants (i.e., participant with completed data on dosing and PK samples) are enrolled.

- **Group #1: "7 doses per week or Perfect Adherence arm"** — cisgender women will receive a single tablet of co-formulated 25 mg TAF/ 200mg FTC once daily (7 doses per week).
- **Group #2: "4 doses per week or Moderate Adherence arm"** — cisgender women will receive a single tablet of co-formulated 25 mg TAF/ 200mg FTC tablet on Monday, Tuesday, Thursday, Friday.
- **Group #3: "2 doses per week or Poor Adherence arm"** — cisgender women will receive a single tablet of co-formulated 25 mg TAF/ 200mg FTC tablet on Monday and Tuesday

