## **7 STATISTICAL CONSIDERATIONS**

### **7.1 Review of Study Design**

An open-label, randomized, three-arm, directly observed therapy, pharmacokinetic study. HIV-uninfected non-pregnant cisgender women will be randomly assigned 1:1:1 to 1 of 3 dosing frequencies of DOT TAF-FTC: 2, 4, or 7 doses/week to help differentiate poor and modest from perfect adherence. Drug concentrations in blood, cervico-vaginal fluid, and tissue will be measured during the study.

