## 7.3 Data Analysis

### 7.3.1 Primary outcomes

**Primary outcome 1:** The goal is to describe the frequency of adverse events, including emergent HIV infection during the study period. We will conduct a descriptive analysis for meeting PrEP157 eligibility among participants. The distribution of demographics and graded adverse events will characterize by overall and study arms and proportions will be compared between study arms using chi-square statistics.

**Primary outcome 2:** The goal is to quantify the effect of dose on steady state TFV-DP in DBS and PBMC based on an incomplete block design.  $C_{ss}$  (drug concentration at steady state) will likely require a normalizing log transform, such that geometric means and CIs will be reported. Dose proportionality will be assessed using the power model (on the natural log scale)  $\ln(Y_{ijk}) = \mu + S_i + P_j + \beta \log(D_k) + \varepsilon_{ijk}$  (Eqn. 1). Where  $Y_{ijk}$  is the response,  $C_{ss}$ , for the  $k$ th dose ( $k=2, 4, 7$  doses/week),  $j$ th period ( $j=1,2$ ),  $i$ th subject ( $i=1, \dots, 45$ );  $\mu$  is the overall mean,  $S_i$  is a random subject effect,  $P_j$  is the period effect and  $\varepsilon_{ijk}$  is random error. Dose proportionality dictates that  $\beta=1$  for dose-dependent parameters and we will assume dose proportionality if the 90% CI is contained within the limits (0.8, 1.25). The SAS mixed procedure will be utilized for model (Eqn 1), again assuming a random subject effect. Although we do not anticipate a period effect, our design allows us to test this effect. For the primary analysis, we assume no effect of 'non-daily dosing' regimens; although this will be examined in a secondary analysis. If dose proportionality is not shown, we will examine proportionality separately for each of the "non-daily dosing" dosing regimens. If dose proportionality is still not demonstrated when adherence regimens are examined separately we will consider dose as a categorical predictor.

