In addition to the power model, we will utilize nonlinear mixed effects models using PK software (NONMEN and/or ADAPT-5) to model drug concentration over time on drug. For this analysis, all available drug concentration samples will be utilized, thereby accounting for missed doses due to protocol deviations. Change in objective function and/or AIC will be used to compare models. This approach will be used to further probe dose proportionality and the final model(s) will be used as a basis for simulation studies.

**Primary outcome 3:** The goal is to identify TFV-DP cut points associated with adherence levels. For the primary analyses, we will attempt to discriminate adherence for 2, 4 and 7 dosing based upon TFV-DP. As above, we will combine the "non-daily dosing" regimens. Linear mixed models with random intercepts, 25th percentiles, and receiver operating characteristics curves will be used to generate predicted concentration thresholds for varying dosing frequency (ranging from 1 to 7 doses/week) for each matrix-analyte pair. Analyses will be adjusted for age, contraception use, study arm, BMI, eGFR, and hematocrit.

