#### 7.5 Randomization and Blinding Procedures

The study design will be an open-label, randomized study with three arms. The randomization assignment will be made at enrollment if the participant is eligible and agrees to enroll. Randomization will be according to the PrEP dosing frequency and vaginal tissue collection plan (either sampling day 4 or day 7) 1:1:1 fashion programmed by the study statistician and generated from REDcap.

The allocation of participants for the 3 study arms will be the following:

	2 doses per week	4 doses per week	7 doses per week	Total
Total	18	18	18	54

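### Primary outcome 3 adjusts for study arm, which is the assigned dosing frequency itself; fitted on assigned dose, the mixed model gives thresholds only at 2, 4 and 7 of the planned 1 to 7 doses/week

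*Combined protocol and SAP*

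**What the plan says.** Under primary outcome 3, Section 7.3.1 names linear mixed models with random intercepts, 25th percentiles and ROC curves. These "will be used to generate predicted concentration thresholds for varying dosing frequency (ranging from 1 to 7 doses/week". The paragraph ends: "Analyses will be adjusted for age, contraception use, study arm, BMI, eGFR, and hematocrit". It does not write the mixed model out, and it does not say whether dose means assigned or taken doses.

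Arm has one definition. Section 2.5 says women "will be randomly assigned to 1 of 3 dosing frequencies of DOT TAF-FTC PrEP", and Section 7.1 says they "will be randomly assigned 1:1:1 to 1 of 3 dosing frequencies of DOT TAF-FTC: 2, 4, or 7 doses/week". Section 7.5 also randomises the biopsy day, but the table introduced by "The allocation of participants for the 3 study arms will be the following" has columns for 2, 4 and 7 doses per week only, with 18 women in each. Section 5.2.1 gives every woman a single 10-week dosing period, so arm and assigned dose never separate within a woman.

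Two neighbouring analyses have no arm term. For primary outcome 2, "Dose proportionality will be assessed using the power model (on the natural log scale", with log dose as a numeric term; the last fallback there is that "we will consider dose as a categorical predictor". The nonlinear PK models are separate again.

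**The concern.** Primary objective 3 is a model that predicts adherence from TFV-DP in DBS. Section 1.1.3 intends the results for reading drug levels in other TAF-FTC PrEP studies. Those studies have no randomised 2/4/7 arm to enter as a covariate, and dosing frequency is the unknown.

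Of the three tools named for this outcome, the mixed model is the natural one for interpolating to 3, 5 and 6 doses/week and extrapolating to 1. Adjusting it for arm removes the between-arm contrast, which is the randomised information on how concentration changes with dosing frequency. What remains depends on an unstated choice of dose variable, and software may settle that choice silently.

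**Working it through.** The plan gives no figure to reproduce here; the check is of model structure.

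**1. Assigned dose plus arm.** Take 18 women at each of 2, 4 and 7 doses/week (Section 7.5), with indicators A4 and A7 for the 4- and 7-dose arms. For every woman

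ln d = ln 2 + (ln 4 − ln 2)·A4 + (ln 7 − ln 2)·A7 = 0.693 + 0.693·A4 + 1.253·A7.

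The dose column is an exact combination of the intercept and the arm columns, so the four columns have rank 3. With slope b and arm effects a4 and a7, the data fix only 0.693b + a4 and 1.253b + a7, never b alone. The three arm means are estimable; a value at 1, 3, 5 or 6 is not. Linear dose gives the same result. Adding age, contraception (taken as one binary term, an assumption), BMI, eGFR and hematocrit gives rank 8 of 9, and a random intercept does not help. In one simulated data set with true slope 1, the reported slope was 0.90, 0.94 or 0.97 according to which arm indicator was kept, and 2.53 with a minimum-norm solution.

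**2. Arm as the dose factor.** Full rank (8 of 8), but it yields three means. Four of the seven planned frequencies have no estimate.

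**3. Doses taken plus arm.** Section 5.2.1 provides a dosing log, so this model is possible and has full rank. Inputs: CV = 601/2381 = 25.2% (Section 7.4, daily dosing; assumed in every arm) and one steady-state value per woman (a simplification).

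- Residual SD on the log scale: σ = √ln(1 + 0.2524²) = 0.2485.
- Without arm: Σ(ln d − 1.342)² = 18 × (0.4207 + 0.0020 + 0.3650) = 14.18, so the slope SE = 0.2485/√14.18 = 0.066.
- With arm, only within-arm variation in ln(doses taken) counts. Scheduled doses missed at random (binomial, rates assumed; simulation medians):

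| Doses missed | Slope SE with arm | Variance inflation |
|---|---|---|
| 1% | 2.05 | 967 |
| 2% | 1.42 | 464 |
| 5% | 0.88 | 180 |
| 10% | 0.60 | 84 |

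Section 3.8 replaces women who miss two consecutive doses or stop, up to 20% of 54 (10.8, so 10 women), and keeps the data of those who discontinue. Adding such women to the same simulations:

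| Added women (share of doses taken, assumed) | Slope SE with arm | Variance inflation |
|---|---|---|
| 2 (20–90%) | 0.25–0.26 | 16–17 |
| 5 (20–90%) | 0.15–0.16 | about 7 |
| 10 (20–90%) | 0.11–0.12 | 4–5 |
| 10 (70–95%) | 0.41–0.44 | 46–54 |

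**4. ROC.** Arm is the class to be separated. Putting it in the score separates the classes by construction, and subtracting arm means from TFV-DP removes the signal by construction. Neither can be used where dosing frequency is unknown.

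**5. Arm removed.** With numeric ln(doses/week) and the other five covariates the rank is 7 of 7, and every value from 1 to 7 is estimable. Ignoring those covariates, the upper 90% limit of the geometric mean at x doses/week is exp{t(0.95, 52)·σ·√[1/54 + (ln x − 1.342)²/14.18]} − 1: +5.8% at x = 4, +9.6% at x = 2 and +17.2% at x = 1, the last being extrapolated.

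**The case against.** A reader might infer that the mixed model cannot produce the 1 to 7 thresholds at all, or that objective 3 is lost. The documents do not support that. Section 7.3.1 writes out no model for this outcome, and one based on logged doses taken is full rank. Random misses alone also overstate the loss of precision: Section 3.8 keeps data from women who discontinue, and Section 4.9 tolerates up to three sequential missed doses. Both add within-arm spread. Random intercepts imply repeated measures, so a model on visit-by-visit dosing history is also conceivable; it was not worked through here.

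Other routes to untested frequencies exist. For the PK models, "the final model(s) will be used as a basis for simulation studies", and Section 7.3.2 uses PK models to simulate other regimens, although for TFV-DP to FTC-TP ratios in a secondary outcome. If proportionality is shown, arm means could be scaled. A statistician would probably notice the aliasing and drop arm.

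All of this limits the size of the point without removing it. The plan does not name the PK simulations as the source of the outcome 3 thresholds, and nothing says arm drops out. Removing a pre-specified covariate of a primary outcome after data are seen would be a deviation. Whether replaced or discontinued women enter this model is also unspecified: Section 2.5 defines evaluable by complete dosing and PK data, and early discontinuers may not be at steady state.

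**Conclusion.** The point holds in conditional form. With assigned dose, or with arm as the dose factor, the mixed model gives values at 2, 4 and 7 and none at 1, 3, 5 and 6; this follows from the design and needs no numerical assumption. With doses taken, the slope is estimable but less precise. Variance inflation is about 84 to 967 under random misses alone and about 4 to 54 in the scenarios with retained women, so the SE is roughly 2 to 31 times larger (√4 = 2; √967 = 31). These ranges rest on assumed adherence patterns and are not bounds.

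Means and 25th percentiles at 2, 4 and 7, an ROC on TFV-DP alone and the PK simulations are unaffected. Data collection and sample size are not in question. The wording should be corrected before analysis because, on the most direct reading, a stated covariate rule blocks a stated primary output.

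**What to change.** In Section 7.3.1, primary outcome 3, delete study arm from the covariate list and keep the other five covariates. Then add:

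> *The linear mixed model for thresholds at 1 to 7 doses/week uses numeric ln(doses/week) as its only dose term, with a random subject intercept and no period term. If the categorical-dose fallback of primary outcome 2 is triggered, mixed-model thresholds are reported at 2, 4 and 7 only. ROC analyses use TFV-DP as the marker, without arm in the score, for binary contrasts of the randomised frequencies (2 vs 4 or more; 4 or fewer vs 7). The threshold at 1 dose/week is labelled as an extrapolation.*

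The model should be stated in full and not by reference to Eqn. 1, which carries a two-period term and 45 subjects, whereas this study has one dosing period and 54 women. The neighbouring sentence that pools the non-daily regimens must be reconciled with separating 2 from 4. The plan should also say whether dose means assigned or taken, and whether replaced or discontinued women enter this model.

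Cost: two words deleted and a few sentences added or clarified, with no change to data collection or sample size.

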DISCOVER used tenofovir diphosphate concentrations (TFV-DP) in DBS to determine adherence to FTC/TDF and TAF-FTC. To interpret adherence, adherence benchmarks were determined in cisgender men and cisgender women in the USA through the DOT-DBS and TAF-DBS studies using directly-observed therapy (DOT). These benchmarks were determined using 2, 4, and 7 DOT doses/ week, has and have proven to be critical for understanding PrEP adherence and efficacy in cisgender men and transgender women. Taken together, TAF is a promising new pro-drug for treatment and as PrEP for prevention of HIV infection, but studies are needed in cisgender women to determine if TFV-DP in DBS will provide the same adherence assessments for TAF as it did for TDF. This due to differing cell pharmacology between TDF and TAF, meaning that TFV-DP in DBS described above from TDF cannot be extrapolated to TAF. Ultimately, we believe that TFV-DP in DBS will have a similar half-life and accumulation as TDF, and will thus provide similar “dose-response” information for TAF-based PrEP, but studies are needed to define TFV-DP in DBS following F-TAF dosing. This protocol is designed to fill that need. The results from this protocol will be used to interpret drug levels and DBS testing that has been incorporated into planned or ongoing TAF-FTC PrEP studies in African cisgender women, where adherence monitoring is a key outcome.

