## 2.3 Primary Objectives

- 1) To describe the safety of TAF-FTC-based PrEP in HIV-uninfected cisgender women.
- 2) To define the cisgender women-specific expected blood concentrations and dose-proportionality for TFV-DP in DBS and PBMCs in cisgender women using directly observed TAF-FTC therapy at 2, 4, 7 doses per week.

- 3) To establish a model to predict adherence rate to TAF-FTC by level of TFV-DP in DBS for cisgender women.

[figure not shown]

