### **7.2 Study endpoints**

- **Aim 1:** Mean, variance, and dose proportionality for TFV-DP or TFV in plasma, DBS, and PBMC for 2, 4, 7 of DOT TAF-FTC dosing per week.
- **Aim 2:** Prediction model of adherence rate by level of TFV-DP in DBS.

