#### 7.4 Sample Size Considerations

The overall sample size was chosen to have up to 18 cisgender women in each relevant group (overall, n=54 non-pregnant cisgender women) sufficient to provide precise information on drug concentrations and to balance feasibility, efficiency, and provide robust TAF/FTC data in DBS for cisgender women. The sample size for drug concentration parameters is based on ensuring precision in the estimates to accurately describe the concentration kinetics of TAF/FTC in non-pregnant cisgender women and is consistent with multiple DOT PrEP studies done in US populations. The precision desired is a mean TFV-DP in DBS at steady state within  $\pm 15\%$  of the true population mean. The mean ( $\pm$  standard deviation) TFV-DP at steady-state in HIV-uninfected US cisgender men and cisgender women following directly observed doses of 25 mg TAF/200mg FTC once daily for 12 weeks was  $2381 \pm 601$  fmol/punches [coefficient of variation (CV) of 25%] (*Anderson et al*). Based on this variability and assuming average TFV-DP results are normally distributed, to be 90% confident that the DBS TFV-DP sample mean is within 15% of the true mean, a sample size of 15 participants is required for non-pregnant cisgender women with conservative assumptions. With the planned enrollment of 18 cisgender women per group for this study, even a 10% non-completion rate at 8 weeks of DOT therapy, we provide ample data to estimate steady-state means to within 10% in cisgender women.

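### Primary outcome 3 adjusts the adherence cut points and ROC curves for patient covariates and names no unadjusted version, although the objective is prediction from the DBS TFV-DP level

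*Combined protocol and SAP*

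**What the plan says.** Section 7.3.1 gives the aim of primary outcome 3: "The goal is to identify TFV-DP cut points associated with adherence levels". Linear mixed models with random intercepts, 25th percentiles and "receiver operating characteristics curves will be used to generate predicted concentration thresholds for varying dosing frequency (ranging from 1 to 7 doses/week". The paragraph ends: "Analyses will be adjusted for age, contraception use, study arm, BMI, eGFR, and hematocrit". No unadjusted counterpart is named there or elsewhere. The text does not say how adjustment enters a percentile or a ROC curve, at which covariate values a threshold is to be read, or which variance components it uses.

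The product is defined without covariates. Section 2.3 has "To establish a model to predict adherence rate to TAF-FTC by level of TFV-DP in DBS for cisgender women", and section 7.2 (Aim 2) has "Prediction model of adherence rate by level of TFV-DP in DBS". Section 1.1.3 says that the results "will be used to interpret drug levels and DBS testing that has been incorporated into planned or ongoing TAF-FTC PrEP studies". The influence of biological variables on concentrations has its own place, in secondary objective 3 (section 2.4) and item 3 of section 7.3.2.

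Study arm, which is also in the adjustment list, raises a separate problem because it is the dosing frequency being discriminated. This point concerns only age, contraception use, BMI, eGFR and hematocrit.

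**The concern.** In a comparison of treatments, covariate adjustment buys precision. In a benchmark that classifies individuals, variation between women is part of the error that the user faces. If age, contraception, BMI, eGFR and hematocrit explain some of that variation and it is removed before the percentile or ROC is formed, the result describes women who share one covariate pattern. Someone who compares a DBS concentration with a single cut point meets the full spread. A lower-percentile cut built on the narrower spread sits too high, so more than the nominal share of fully adherent women fall below it, and the AUC looks better than that user can achieve. What is at stake is how adherence is read in the later trials that adopt these benchmarks.

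**Working it through.** **Inputs from the documents.** Section 7.4 gives a mean of 2381 and an SD of 601 fmol/punches on daily dosing. The CV is 601/2381 = 25.2%, which agrees with the stated 25%. Section 7.3.1 expects a log transform. There are 18 women per arm (sections 7.4 and 7.5). The documents state no cut point, AUC or error rate, so there is no plan figure for this outcome to reproduce.

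**Assumptions.** Concentrations are lognormal with the same log SD in every arm; arm means are dose-proportional; each woman contributes one steady-state value; and the CV, which comes from US men and women on daily dosing, carries over. R² is the share of within-arm log variance that the covariates explain. The documents do not give it, so it is varied from 0 to 50%.

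**Formulas.**
- Log SD: s = √ln(1 + 0.2524²) = 0.2485. Geometric mean, daily arm: 2381/√(1 + 0.2524²) = 2309.
- Conditional SD: s_c = s√(1 − R²).
- 25th-percentile cut: 2309 × exp(−0.6745 s_c).
- Share of daily users below that cut when they face the full spread: Φ(−0.6745 s_c/s).
- AUC, 4 versus 7 doses: Φ(ln(7/4)/(√2 s_c)), with ln(7/4) = 0.560.

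| R² | s_c | Daily 25th percentile | Shift | Daily users below it | AUC 4 v 7 | AUC rise |
|---|---|---|---|---|---|---|
| 0 | 0.2485 | 1952 | 0 | 25.0% | 0.944 | 0 |
| 10% | 0.2358 | 1969 | +0.9% | 26.1% | 0.953 | 0.009 |
| 30% | 0.2079 | 2006 | +2.8% | 28.6% | 0.971 | 0.027 |
| 50% | 0.1757 | 2051 | +5.0% | 31.7% | 0.988 | 0.044 |

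The R² = 0 row is what a user of the concentration alone would obtain.

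**In-sample fitting.** A simulation of 54 women with five covariates (4,000 runs) formed the cut and the ROC from covariate-adjusted values in the same data. The 4-versus-7 AUC rose from about 0.945 to 0.953, 0.961, 0.977 and 0.991 at R² of 0, 10, 30 and 50%. The cut rose by 0.8, 1.5, 3.1 and 5.0%. So there is some optimism even when the covariates carry no information.

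**Sampling error for comparison.** The log-scale standard error of a parametric 25th percentile in 18 women is 0.2485 × √(1/18 + 0.6745²/(2 × 17)) = 0.065, or about 6.5%. By simulation it is about 7.6% for an empirical percentile. The simulated standard error of the 4-versus-7 AUC is about 0.036. The cut shift stays below its standard error across the whole range. The AUC rise reaches 0.036 at an R² of about 40% (AUC 0.980) and exceeds it only beyond that.

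**The case against.** The strongest reply is that the harm depends on a method the plan does not state. Empirical 25th percentiles of observed concentrations, or predictions averaged over the covariates with total variance, would not move. This stands. A reader might infer from the adjustment sentence that accuracy is overstated and the cut too high as a matter of fact; the documents do not support that, because they leave the use of adjustment open.

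A reader might also take it as stated that users will have only a DBS value. The documents do not say so, and the receiving trials may hold age, BMI, contraception, creatinine and hematocrit. The inference rests on objective 3, Aim 2 and section 1.1.3, none of which names a covariate as an input.

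The size is unsourced as well. Eligibility narrows some covariates (age 18 to 30, eGFR above 60 mL/min, hemoglobin above 10 g/dL), so R² could be small; at 10% the cut moves by 0.9%. Nor does chance fit bias every threshold. With 7 covariate degrees of freedom and 51 within-arm degrees of freedom, the expected null R² is 7/51, about 14%. However, a residual SD corrected for degrees of freedom does not inherit it: in simulation it stayed at about 0.248 with and without seven null covariates. Only cuts or ROC curves built on raw in-sample residuals would be affected.

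Finally, Aim 1 already reports the mean and variance of TFV-DP by dosing frequency, and the power model contains none of these covariates. That supplies ingredients for an unadjusted percentile. It does not make the primary outcome 3 thresholds or ROC unadjusted, and the adjustment sentence in section 7.3.1 makes no exception for them.

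**Conclusion.** The concern holds as a mismatch between objective and analysis, with a conditional and modest numerical consequence. The plan requires adjustment, names no unadjusted threshold or ROC, and defines its product as prediction from the DBS level. If covariate-conditional variance is used, the daily-arm 25th-percentile cut is 0 to 5.0% too high and the 4-versus-7 AUC is overstated by 0 to 0.044 for R² from 0 to 50%, with some further optimism if raw residuals are used. Those figures rest on the assumed R², a log SD of 0.2485 in all arms and dose-proportional means. Over most of the range they are smaller than sampling error. Sampling error, though, is visible in a confidence interval; a mismatch between the conditional and the total spread is not, and it does not shrink with more women.

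**What to change.** State in section 7.3.1 that the primary thresholds, percentiles and ROC curves are unadjusted: DBS TFV-DP against dosing frequency only, using total (between- plus within-woman) variance. Move the models with age, contraception use, BMI, eGFR and hematocrit to secondary objective 3 as a sensitivity analysis, and state the reference covariate values and the variance components used for any threshold they yield.

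This is a short text change and needs no new data, visits or participants. The price is that reported accuracy may be slightly less favourable than under a covariate-conditional analysis.
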